# **13 STATISTICAL CONSIDERATIONS**

# 13.1 Statistical Methods

# 13.1.1 Primary Endpoint

The primary outcome in this study is non-relapse mortality (NRM) at one year.

## 13.1.2 Secondary Endpoints (with measurement type)

- Time to engraftment (in days)
- Acute GVHD (days to positive diagnosis: time-to-event; positive diagnosis: categorical)
- AEs of grade ≥ 3 possibly, probably, or definitely related to the vitamin C regimen (counts by event type)

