#### 2.2 Secondary Objectives

In patients who have had myeloablative allogeneic HCT:

- 2.2.1 To determine the effect of the vitamin C regimen on the time to hematopoietic engraftment
- 2.2.2 To determine the effect of the vitamin C regimen on the rate of acute GVHD
- 2.2.3 To characterize the safety and tolerability of the vitamin C regimen

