#### 3.3 Secondary Endpoints

- 3.3.1 Number of days from transplant to hematopoietic engraftment
- 3.3.2 Proportion of patients with a diagnosis of acute GVHD
- 3.3.3 Adverse events (AEs) reported using criteria in the National Cancer Institute Common Terminology Criteria for Adverse Events Version 5.0 (CTCAE v5.0)

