## 6.1.2 Planned Vitamin C Regimen

All study patients will receive the following vitamin C regimen:

- Parenteral vitamin C 50 mg/kg/day divided in 3 doses beginning on posttransplant Day +1 and continuing through Day +14; each dose (16.7 mg/kg) given in 50 mL of 5% dextrose and water over 30 minutes every 8 ± 3 hours
- After completion of the parenteral vitamin C doses, oral vitamin C 500 mg twice each day beginning on Day +15 and continuing until Day +180

The vitamin C regimen will continue as described above even if the vitamin C levels are found to be within normal range at the time of testing (refer to Section 6.3 for testing time points).

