## 8.4 Time Period and Grade of AE Capture

AEs  $\geq$  grade 3 regardless of expectedness or attribution will be recorded for study tabulation and analysis beginning on Day 0 and continuing until Day 180. Toxicity assessments will include a review of all toxicities experienced during each assessment period. The highest grade of each relevant toxicity during that period will be recorded.

Exception: Cytopenias and changes in electrolytes will **not** be recorded. Only clinical events and lab values reflecting renal function (eg, creatinine, urinalysis results) will be recorded as AEs.

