# 8.5 AEs Requiring Expedited Reporting

All patients in this study will be receiving potentially toxic preparative therapy, therefore, significant regimen-related toxicity is anticipated, ie, expected AEs.

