## 13.1.4 Statistical Analysis

The primary and secondary outcomes will be compared between the study cohort and a historical cohort matched for age, donor type, and diagnosis. The NRM rate will be compared to the historical 35% rate (see Section 13.2 below) using a onesided exact binomial test. Time-to-event outcomes (time to engraftment, acute and chronic GVHD, and overall and relapse-free survival) will be graphically represented with a Kaplan-Meier step-function and will be assessed for associations with serum vitamin C levels and patient demographic measurements using a Cox Proportional Hazards model. Associations between blood levels of vitamin C and other exploratory endpoints will be estimated using Spearman rank correlation coefficients.

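### The secondary safety endpoint counts only adverse events attributed to vitamin C, so the planned comparison with a historical cohort is uninformative

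*Combined protocol and SAP*

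**What the plan says.** The safety objective in Section 2.2.3 is "To characterize the safety and tolerability of the vitamin C regimen". Section 3.3.3 gives the matching endpoint as "Adverse events (AEs) reported using criteria in the National Cancer Institute Common Terminology Criteria for Adverse Events Version 5.0 (CTCAE v5.0"), with no limit by attribution or grade. Section 13.1.2 narrows it to events of grade 3 or higher that are "possibly, probably, or definitely related to the vitamin C regimen (counts by event type").

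Section 13.1.4 opens: "The primary and secondary outcomes will be compared between the study cohort and a historical cohort matched for age, donor type, and diagnosis". No secondary outcome is excepted.

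The trial has one arm; Section 6.1.2 begins "All study patients will receive the following vitamin C regimen". Section 8.1.8 defines attribution as a judgement about the study intervention, and the lowest category that counts is Possible. Section 8.4 is broader than Section 13.1.2: from Day 0 to Day 180, events of grade 3 or higher "regardless of expectedness or attribution will be recorded for study tabulation and analysis". It excepts cytopenias, electrolyte changes and other laboratory values that do not reflect renal function. Section 8.5 says of the whole study population that "significant regimen-related toxicity is anticipated".

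**The concern.** Read together, Sections 13.1.2 and 13.1.4 ask for a comparison of events attributed to vitamin C between patients who received the regimen and patients who did not. The second group cannot contribute an event under that definition, however much toxicity it had.

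Without the comparison, the attributed count is still a weak main summary. Some events could come from either source. Diarrhea is a known effect of vitamin C in Section 8.2 and a common post-transplant event in Section 8.5.2. Renal calculi are a stated risk in Section 9.1, and renal insufficiency is on the Section 8.5.2 list. With no concurrent control, nothing in the data tests the investigator's call.

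At stake is the interpretability of one secondary endpoint, the only one that serves the safety objective.

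**Working it through.** The plan states no power, rate or test for this endpoint, so there is no figure to reproduce. The check is one of definitions.

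**1. What the historical cohort can contribute.** An event counts only if it is attributed to the study intervention (Sections 8.1.8 and 13.1.2). Assume that the historical patients were not given the study regimen, which the comparison presupposes. Their count is then 0 for every event type, whatever their toxicity.

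**2. What the difference would measure.** For one event type, let n be the number of study patients and define:
- b: background risk of the event per patient
- e: extra risk caused by vitamin C
- f: share of background events called at least possibly related
- s: share of vitamin C-caused events called at least possibly related

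Then:
- Expected attributed count in the study: n(bf + es)
- Historical count: 0
- Difference shown by the plan: n(bf + es) − 0 = n(bf + es)
- True excess: ne
- Error: n(bf + es) − ne = n[bf − e(1 − s)]

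Two limiting cases show that the error has no fixed sign:
- If vitamin C does no harm (e = 0), the plan shows nbf, which is above zero whenever any background event is called possible.
- If no background event is attributed (f = 0), the plan shows nes, which is below ne whenever s is less than 1.

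The historical cohort's own risk appears nowhere in the difference, so matching on age, donor type and diagnosis cannot help. The documents give none of b, e, f or s for grade 3 or higher events.

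**3. The same comparison on all-cause events.** The expected study proportion is b + e. If matching gives the historical cohort the same background risk b, the difference is (b + e) − b = e. That is the quantity of interest, but it requires historical events graded and captured in the same way. The documents do not say that such data exist.

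**4. Scope across sections.**
- Section 3.3.3: adverse events by CTCAE v5.0, any attribution.
- Section 8.4: grade 3 or higher, any attribution, Day 0 to Day 180.
- Section 13.1.2: grade 3 or higher, attributed events only.
- Section 13.3: five grade 4 toxicities, each counted separately, with no attribution condition.

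Of these, only Section 13.1.2 requires attribution.

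**5. Does it reach the stopping rules?** No. Tables 6 and 7 count the five grade 4 toxicities against a fixed null of 0.30. Tables 6 and 8 count ANC engraftment failures against 0.10. Neither rule uses attribution or the historical cohort.

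**6. Timing.** Section 8.4 starts capture on Day 0, while Section 6.1.2 starts vitamin C on Day +1. The capture window therefore includes events that precede exposure, and an all-cause table has to identify them.

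**The case against.** The strongest reply is that the comparison sentence was never meant for adverse events. After it, Section 13.1.4 names methods for NRM (one-sided exact binomial), for time-to-event outcomes (Kaplan-Meier and Cox) and for biomarker associations (Spearman). It names none for adverse events, whose measurement type in Section 13.1.2 is a count by event type. A descriptive tabulation caught by a loosely worded sentence is a plausible reading. This limits the likely harm, but the text excepts nothing, and the mismatch with Section 3.3.3 remains on either reading.

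Four stronger readings are tempting, and the documents do not support them:

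- **The plan guarantees a false safety signal.** That would need a test against the structural zero, and no test is specified.
- **The plan hides harm.** Section 8.4 captures all-cause grade 3 or higher events for tabulation and analysis, and the DSMC reviews toxicity and engraftment after the 14-patient lead-in. Possible is a low threshold, so over-attribution is as open as under-attribution.
- **Section 13.1.2 contradicts Section 8.4.** Section 8.4 is a capture rule, and analysing a subset of what is captured does not breach it. The mismatch to reconcile is with Section 3.3.3.
- **The distortion can be sized from the plan's 30% toxicity rate.** For 55 patients, 0.30 × 55 = 16.5 events of one type. But 0.30 is a stopping-rule null for each of five grade 4 toxicities, not a background rate for grade 3 or higher events, and any attribution share would be invented.

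**Conclusion.** The point holds as a defect of definition. Applied literally, Sections 13.1.2 and 13.1.4 produce a comparison with a group whose count is fixed at zero, which carries no information about the risk of vitamin C. This rests on one assumption, that the historical patients did not receive the study regimen. Separately, the attribution limit does not match Section 3.3.3, and it makes the main safety summary depend on judgements that a single-arm trial cannot check.

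No numerical magnitude can be drawn from the documents, and the direction of error is undetermined. The effect is confined to one secondary endpoint. It is worth correcting before analysis because the study data needed for a better endpoint are already collected. It is not evidence that patient safety is unmonitored or that harm would be concealed.

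**What to change.** **Section 13.1.2.** Define the endpoint as all grade 3 or higher adverse events recorded under Section 8.4, regardless of attribution. Count patients with at least one event, by event type, over the Section 8.4 window. Counting patients avoids counting one patient more than once when the same toxicity is recorded in several assessment periods. Identify events that occur before the first vitamin C dose, and list the related subset descriptively. Align the wording of Section 3.3.3.

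**Section 13.1.4.** State that adverse events are summarised descriptively and are not compared with the historical cohort. Allow one exception: if comparably graded all-cause data exist for that cohort, compare all-cause events only.

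**Cost.** The change needs one bullet, one clause and a matching edit to Section 3.3.3. It needs no new data from study patients. The safety table becomes slightly longer, and there is no formal adverse event comparison if historical data are lacking.

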# 13.1.3 Exploratory Endpoints

- Chronic GVHD (days to positive diagnosis: time-to-event; positive diagnosis: categorical)
- Overall survival
- Relapse-free/GVHD-free survival
- Levels in blood over time of vitamin C and exploratory biomarkers

## 13.1.4 Statistical Analysis

The primary and secondary outcomes will be compared between the study cohort and a historical cohort matched for age, donor type, and diagnosis. The NRM rate will be compared to the historical 35% rate (see Section 13.2 below) using a onesided exact binomial test. Time-to-event outcomes (time to engraftment, acute and chronic GVHD, and overall and relapse-free survival) will be graphically represented with a Kaplan-Meier step-function and will be assessed for associations with serum vitamin C levels and patient demographic measurements using a Cox Proportional Hazards model. Associations between blood levels of vitamin C and other exploratory endpoints will be estimated using Spearman rank correlation coefficients.

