# 10.2 Length of Relapse-Free/GVHD-Free Survival and Survival

All study patients including those removed from the treatment protocol will be followed for survival every 3 months.

- Length of relapse-free/GVHD-free survival is measured from transplant to relapse, GHVD diagnosis, death, or time of last contact, censoring for patients alive and relapse-free/GVHD-free at the time of last contact.
- Length of survival is measured from transplant to death or time of last contact, censoring for patients alive at time of last contact.

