#### 13.3.2 Stopping Criteria for Phase 2 portion

If criteria are met to proceed to the phase 2 portion of the trial, the rates of engraftment failures and severe toxicities will continue to be monitored, and the early stopping rules outlined in Table 7 and Table 8 will be employed.

The stopping rules for the phase 2 portion of the study are based on an exact binomial test using the null proportion of 0.30 for each of the five toxicities listed above and a one-sided, right-tailed significance level of  $\alpha$ =0.05 for sample sizes 2 to 55 (Table 7).

ANC engraftment failure will also be used for a stopping rule based on an exact binomial test using the null proportion of 0.10 for engraftment failure and a one-sided right-tailed significance level of  $\alpha$ =0.05 for sample sizes 4 to 55 (Table 8). ANC engraftment failure is defined as failure to achieve hematopoietic engraftment (Section 10.1) within 30 days after transplant.

Accrued Sample Size	Stopping Rule
15-17	8
18-20	9
21-22	10
23-25	11
26-28	12
29,30	13
31-33	14
34-36	15
37-39	16
40,41	17
42-44	18
45-47	19
48-50	20
51-53	21
54,55	22

 Table 7. Number of Observed Toxic Events (Measured Separately for Each Toxicity

 Outcome) Needed to Stop Phase 2 Portion of Trial Given Accrued Sample Size

 Table 8. Number of Observed ANC Engraftment Failures Needed to Stop Phase 2

 Portion of Trial Given Accrued Sample Size

Accrued Sample Size	Stopping Rule
15-20	4
21-27	5
28-34	6
35-41	7
42-48	8
49-55	9

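### Engraftment and GVHD are to be drawn as Kaplan-Meier curves with no rule for death before the event; if those deaths are censored, the curves overstate incidence, by about 1 to 4 points for the secondary endpoints under assumed early-death rates.

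*Combined protocol and SAP*

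**What the plan says.** Section 13.1.4 gives five outcomes one method: "Time-to-event outcomes (time to engraftment, acute and chronic GVHD, and overall and relapse-free survival) will be graphically represented with a Kaplan-Meier step-function". The same outcomes are then examined for association with serum vitamin C and "patient demographic measurements using a Cox Proportional Hazards model".

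Two of the five are secondary endpoints. Section 3.3 defines the engraftment endpoint as "Number of days from transplant to hematopoietic engraftment" and the acute GVHD endpoint as "Proportion of patients with a diagnosis of acute GVHD". Section 13.1.2 lists acute GVHD both as a time-to-event and as a categorical measure. Chronic GVHD is exploratory (Section 13.1.3). Section 13.1.4 also states: "The primary and secondary outcomes will be compared between the study cohort and a historical cohort matched for age, donor type, and diagnosis".

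Section 10.2 has event and censoring rules for relapse-free/GVHD-free survival, where death is an event and the rule is "censoring for patients alive and relapse-free/GVHD-free at the time of last contact", and for survival. Section 10.1 defines engraftment and Section 10.4 defines GVHD grading. Neither says what happens to a patient who dies first. Competing risks and cumulative incidence are not mentioned anywhere.

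**The concern.** Death before engraftment or GVHD is a competing event. A Kaplan-Meier curve that censors it treats the dead patient as someone who could still have the event later, so one minus the curve is larger than the fraction of patients who have it. The direction is fixed: any censored death before the event pushes the curve upward. More patients will not remove the excess.

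It matters here because mortality is what the trial hopes to change. Section 13.2 sets one-year NRM at 35% under the null and 20% under the alternative. If treatment works as hoped, the excess differs between the study cohort and the historical cohort, and part of any difference read from the curves would be an artefact. The acute GVHD curve would also disagree with the acute GVHD proportion in the same report. For GVHD, the plan does not say whether relapse censors, competes or is ignored.

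**Working it through.** **The plan's own figures.** The documents give no figure for these curves. The one calculation they do give, the two-stage design in Section 13.2, reproduces: continuing with at most 10 NRMs in 31 patients and rejecting with at most 13 in 55 gives a one-sided error of 0.0484 at 35% and power of 0.8006 at 20%. It does not depend on the curves.

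**Inputs from the documents**
- Acute GVHD 35-50% and chronic GVHD 40-70% (Section 1.1).
- Engraftment 90% by day 30, the complement of the stopping-rule null: "using the null proportion of 0.10 for engraftment failure" (Section 13.3.2).
- One-year NRM 35% and 20%, n = 55 (Section 13.2).

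**Assumed.** D, the proportion dying before the event: 5-10% for acute GVHD and 1-5% for engraftment.

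**Formula.** Let F be the true incidence. With constant hazards, the total cumulative hazard is H = −ln(1 − F − D), the event's share of it is F/(F + D), and

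1 − KM = 1 − exp(−H × F/(F + D)).

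Example: F = 0.35, D = 0.10. H = −ln(0.55) = 0.598, share = 0.778, so 1 − KM = 1 − exp(−0.465) = 0.372.

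| Endpoint | F | D | 1 − KM | Excess (points) |
|---|---|---|---|---|
| Acute GVHD | 35% | 5% | 36.0% | 1.0 |
| Acute GVHD | 35% | 10% | 37.2% | 2.2 |
| Acute GVHD | 50% | 5% | 51.6% | 1.6 |
| Acute GVHD | 50% | 10% | 53.4% | 3.4 |
| Engraftment | 90% | 1% | 90.8% | 0.8 |
| Engraftment | 90% | 2% | 91.6% | 1.6 |
| Engraftment | 90% | 5% | 94.2% | 4.2 |

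**Are the assumed death rates reasonable?** At a constant hazard, one-year NRM of 20% and 35% implies 1 − 0.80^(100/365) = 5.9% and 1 − 0.65^(100/365) = 11.1% dead by day 100. This supports 5-10% for acute GVHD. By day 30 it implies only 1.8% and 3.5%, engrafted or not, so 5% dying before engraftment needs deaths concentrated early.

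**Sensitivity**
- Death hazard set from 20-35% one-year NRM: excess 0.5-1.0 points for engraftment and 1.0-2.6 for acute GVHD to day 100.
- Half of that NRM falling by day 100: 1.7-4.3 for acute GVHD.
- Engraftment with a 12-day lag and 1-5% early deaths: about 0.9-4.6.
- Letting D for acute GVHD run from 2% to 15%: 0.4-5.4.

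**Between cohorts.** Take D for the historical cohort and D × 20/35 for the study cohort, with the same true acute GVHD incidence in both.
- F = 35%: 36.0% against 35.6% (D = 5%), 37.2% against 36.2% (D = 10%).
- F = 50%: 51.6% against 50.9% (D = 5%), 53.4% against 51.9% (D = 10%).

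The artefact is 0.5-1.5 points. The standard error of a 40% proportion at n = 55 is √(0.4 × 0.6/55) = 6.6 points.

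**Whole patients, n = 55, event order random.** With 22 acute GVHD cases (40.0%) and 6 prior deaths, 1 − KM averages 42.8%. With 50 engrafted (90.9%) and 3 prior deaths, it averages 95.6%.

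**Chronic GVHD (exploratory), F = 40%.** If a quarter, half or all of NRM precedes it, the excess is 2.2, 4.9 or 12.3 points at 35% NRM, and 1.2, 2.6 or 5.7 at 20%.

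**The case against.** The strongest reply is that no planned test is shown to use the biased quantity. Kaplan-Meier is assigned to graphical display. The Cox model, with deaths censored, validly estimates cause-specific hazard ratios. Acute GVHD is also defined as a proportion, which is unaffected if every patient stays in the denominator. The sentence on the historical cohort does not say that the comparison runs through the curves. The plan never says that deaths will be censored. The early-death rates are not in the documents, and 90% engraftment is a stopping-rule null, not an expected rate. The between-cohort artefact for acute GVHD is below one patient in 55 (1.8 points).

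Most of this is right, and it limits the weight of the point. The primary test, the sample size and the safety rules are untouched. The upper engraftment figure needs early deaths to be concentrated, and the 12.3-point chronic GVHD figure is an extreme, since Section 1.1 names GVHD itself as a usual cause of NRM.

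What remains is that a plan naming Kaplan-Meier and silent on death will ordinarily be carried out by censoring it. Time to engraftment is a secondary outcome with no planned proportion beside it in Section 13.1.2. Published curves get read as incidences, and the error always has the same sign.

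**Conclusion.** The point holds. The omission and the direction of the error are certain, provided some deaths precede the event and are censored. The size is conditional: about 1 to 4 points for the secondary endpoints under constant hazards, with 5-10% dying before acute GVHD and 1-5% before engraftment. Letting deaths before acute GVHD run from 2% to 15% widens this to 0.4-5.4 points. Chronic GVHD can be further off, but it is exploratory and outside the historical comparison. The excess is smaller than sampling error at n = 55, so this is a correction the plan should make and not a threat to the design or the primary conclusion.

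**What to change.** - Keep Kaplan-Meier for overall and relapse-free/GVHD-free survival.
- Present engraftment and acute and chronic GVHD as cumulative incidence (Aalen-Johansen) with death as a competing event.
- State whether relapse also competes for GVHD, and give the censoring rule for each endpoint.
- Apply the same estimator to the historical cohort for the secondary outcomes.
- Label Cox results for these endpoints as cause-specific hazard ratios.

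The cost is SAP wording. The software is standard and the study data are already to be collected. The historical cohort needs dates of the event and of death; the planned comparison of time to engraftment already presupposes event times there.

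One caution: cumulative incidence can rise simply because fewer patients die first. If deaths before acute GVHD fall from 10% to 5.7% (10% × 20/35) with the GVHD hazard unchanged, true incidence rises from 35.0% to 35.9%, or from 50.0% to 51.5%, while one minus Kaplan-Meier stays at 37.2% or 53.4%. Reporting the cause-specific hazard ratio beside the cumulative incidence guards against misreading this.

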# 1 BACKGROUND

# 1.1 Introduction

Approximately 20,000 hematopoietic cell transplants (HCT) are performed in the United States each year (Pasquini MC. 2014 CIBMTR Summary Slides). Myeloablative allogeneic HCT remains the only potential cure for leukemia, lymphoma, and hematopoietic disorders, however, it is associated with a high risk of morbidity and mortality. Myeloablative conditioning (MAC) refers to the necessary chemotherapy and/or radiation regimen used in stem cell transplant to eliminate residual leukemia/lymphoma and condition the host for the incoming graft of hematopoietic stem cells (HSC).

Non-relapse mortality (NRM), defined as mortality from complications of HCT but not tumor relapse, is usually from graft versus host disease (GVHD), infection, or organ failure. NRM after allogeneic HCT is influenced by type of donor (related vs. unrelated), conditioning chemotherapy doses, and co-morbidities of the recipient. In a study reported by Sorror et al, 2-year NRM in myeloablative allogeneic HCT was 14% to 41% based on patient comorbidities (1). In a recent clinical trial (BMTCTN 0901) comparing conditioning chemotherapy regimens of different intensities in acute myelogenous leukemia (AML), the overall NRM was 16% at 18 months (2).

HCT after myeloablative conditioning has several associated toxicities such as pancytopenia, mucositis, interstitial pneumonitis, hepatic sinusoidal obstruction syndrome/veno-occlusive disease (SOS/VOD), and sepsis. These HCT toxicities are induced by MAC and are characterized by endothelial injury and a pro-inflammatory state with elevated inflammatory cytokines such as IL-1 and tumor necrosis factor-alpha (TNF- $\alpha$ ) (3). The inflammatory response increases antigen presenting cell (APC) activity presenting minor histocompatibility antigens to T-cells resulting in acute GVHD in 35-50% of HCT recipients. Acute GVHD is a leading risk factor for chronic GVHD which is present in 40-70% of all HCT (3). GVHD, infection, and organ failure as a consequence of HCT contributes to NRM after allogeneic HCT. The one-year NRM at Virginia Commonwealth University (VCU) in 2014-2015 was 10-20% for patients receiving HLA-matched related donor grafts (MRD) and 20 - 40% in those with unrelated donor grafts (MUD) (4, 5).

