# 6 TREATMENT PLAN

## 6.1 Study Treatment

6.1.1 Safety Lead-In Cohort

For the initial safety lead-in cohort of 14 patients, vitamin C deficiency will be confirmed by a standard clinical pathology laboratory blood test before the first dose of parenteral vitamin C (see Sections 12 and 13.3). Safety lead-in patients with confirmed vitamin C levels of 0.5 mg/dL or less (20) may proceed on study treatment.

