# 13.2 Sample Size and Power Determination

The sample size and power are calculated based on Simon's two-stage minimax design, which minimizes the expected maximum sample size under the alternative hypothesis. The previous 2 years at VCU have seen an ~15% NRM rate in MRD patients and an ~40% NRM rate in MUD patients. Given that MRDs comprise ~25% of total transplantations and MUDs comprise ~75%, we then assume an overall 35% NRM rate. The null hypothesis that the NRM rate is 35% will be tested against a one-sided alternative. In order to achieve 80% power (with 5% significance) to declare an NRM of 20% significantly smaller than the

hypothesized null NRM of 35%, we will accrue 31 patients in stage 1 and an additional 24 patients in stage 2 (provided the trial is not stopped early for futility). At the end of stage 1, if there are 11 or more NRMs in the 31 stage 1 patients, the study will be stopped for futility. Otherwise, 24 additional patients will be accrued for a total of 55. The null hypothesis will not be rejected if 14 or more NRMs are observed in the total 55 patients. We anticipate a 32% screen failure rate, leading to a recruitment target of 81 subjects (VCU sees ~5 eligible MRD/MUD patients per month). The number of MUD patients will be limited to 80%.

The population evaluable for the primary endpoint includes all patients who receive at least one dose of IV vitamin C and who have a known survival status at one year. Patients who are enrolled to the study but do not receive any IV vitamin C or who are lost to follow up at one year will be replaced.

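### The Cox models in Section 13.1.4 name vitamin C level and demographics but not donor type, a strong prognostic factor that the trial already records

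*Combined protocol and SAP*

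**What the plan says.** Section 13.1.4 assigns the Cox model to "Time-to-event outcomes (time to engraftment, acute and chronic GVHD, and overall and relapse-free survival") and says that these "will be assessed for associations with serum vitamin C levels and patient demographic measurements using a Cox Proportional Hazards model". No other term is named. The text does not say whether the model is univariable or multivariable. NRM is not on this list; it has its own exact binomial test.

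Donor type does appear in the same paragraph, but only for the comparison with "a historical cohort matched for age, donor type, and diagnosis".

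Elsewhere the protocol treats donor type as prognostic. Section 1.1: "NRM after allogeneic HCT is influenced by type of donor (related vs. unrelated), conditioning chemotherapy doses, and co-morbidities of the recipient". Section 13.2: "The previous 2 years at VCU have seen an ~15% NRM rate in MRD patients and an ~40% NRM rate in MUD patients". Section 13.2 also gives the mix ("MRDs comprise ~25% of total transplantations and MUDs comprise ~75" per cent) and a cap ("The number of MUD patients will be limited to 80" per cent), which cannot be applied without recording donor type for each patient.

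**The concern.** The trial has one arm. The models relating vitamin C level to engraftment, GVHD and survival are the only planned analysis that looks within the cohort for a link between the vitamin and time-to-event outcomes, so a protective hazard ratio there could easily be read as supporting efficacy.

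A factor that predicts outcome and is left out of such a model biases the vitamin C coefficient if it is also related to vitamin C level. The protocol's own figures supply the outcome link for donor type. If unrelated-donor patients tend to have lower levels, an inactive vitamin would look protective. The plan controls for donor type when it looks outward to historical patients and does not name it when it looks inward. The omission stands whether the model is univariable or contains exactly the named terms.

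**Working it through.** **Inputs from the documents.** NRM about 15% (related) and 40% (unrelated); mix 25%/75%; N = 55 (all Section 13.2). Acute GVHD in 35–50% of recipients (Section 1.1). Survival follow-up of 2 years (Section 6.5.3).

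**Inputs assumed.** The gap in vitamin C level, unrelated below related, in SD units: 0 to 0.8. No true vitamin C effect. Constant hazards. For the survival set-up, a 15% per year risk of death from other causes, the same for both donor types.

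**1. The plan's own figure.** 0.25 × 15% + 0.75 × 40% = 3.75% + 30% = 33.75%, which Section 13.2 takes as 35%. The two donor rates are therefore the basis of the trial's null value. The documents give no event count or power for the Cox models.

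**2. Strength of donor type.** Implied NRM hazard ratio, unrelated vs related: ln(1 − 0.40) / ln(1 − 0.15) = (−0.511) / (−0.163) = 3.14.

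**3. Events.**
- Outcome at NRM-like rates over one year: 0.3375 × 55 = 18.6.
- Acute GVHD: 0.35 × 55 to 0.50 × 55, about 19 to 28.
- Two-year survival set-up: the unrelated hazard is 0.511 + 0.163 = 0.673 per year, so 1 − exp(−1.347) = 0.740; the related hazard is 0.163 + 0.163 = 0.325, so 1 − exp(−0.650) = 0.478. Deaths: 55 × (0.75 × 0.740 + 0.25 × 0.478) = 37.

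**4. Simulated Cox fits at N = 55, two-sided 5% Wald test.**

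Outcome at NRM-like rates, one year, about 19 events, 3,000 replicates per row:

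| Assumed gap (SD) | HR per SD, no donor term | False positives | HR per SD, donor term | False positives | SE of vitamin C coefficient, without → with |
|---|---|---|---|---|---|
| 0 | 1.01 | 5.6% | 1.00 | 5.4% | 0.234 → 0.238 |
| 0.25 | 0.96 | 5.5% | 1.00 | 4.7% | 0.235 → 0.238 |
| 0.5 | 0.92 | 6.1% | 0.99 | 5.3% | 0.234 → 0.241 |
| 0.8 | 0.87 | 8.0% | 1.00 | 4.7% | 0.235 → 0.250 |

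Two-year survival, about 37 deaths: HR about 0.94–0.95 for a 0.5 SD gap and 0.91–0.93 for 0.8 SD, with false-positive rates of about 5–9%. With donor type in the model the HR returns to about 1.00. With no gap it is 0.99 and the rate 5.8%, which is nominal within simulation error.

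Simulation error on a rate near 8% with 3,000 replicates is √(0.08 × 0.92 / 3000), about half a percentage point.

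**5. Price of the donor term.** 0.241 / 0.234 = 1.03 and 0.250 / 0.235 = 1.06 in the table. Across the runs the standard error rises by about 2–7% for gaps of 0.5 to 0.8 SD.

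**6. Price of a lead-in term.** With a level gap of 0.8–1.2 SD between lead-in and later patients and no outcome difference, omitting the term gives no bias (HR about 1.00, error 4.9%). Including it raises the standard error from about 0.237 to 0.256–0.272, that is by 8–15%.

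**The case against.** **The sentence does not describe an adjusted model.** It lists vitamin C and demographics together as factors to be examined. A reader might infer that the plan adjusts for demographics and deliberately excludes everything else. The text does not go that far: the model form is unstated. This objection stands, and the finding is that donor type is not named. It does not remove the gap, because donor type is missing on either reading.

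**One of the two links is missing.** No section reports vitamin C level by donor type. This stands; with no gap there is no bias.

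**The 3.14 is for NRM, which is not a Cox outcome here.** This also stands. NRM deaths do count in overall and relapse-free survival, so the link carries over in diluted form, but its strength for GVHD and engraftment is unknown. Nor do the documents show donor type to be the dominant factor: Section 1.1 lists it beside conditioning dose and comorbidity without ranking them.

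**Lead-in membership.** A reader might infer that it must also be a covariate, since Section 6.1.1 lets "Safety lead-in patients with confirmed vitamin C levels of 0.5 mg/dL or less" proceed and later patients have no such limit. The documents do not support that:
- No section links lead-in status to outcome, and selection on level alone does not bias the coefficient.
- The limit applies to a separate lead-in-only test 2 to 5 days before transplant (Table 4), not to a scheduled study sample (baseline before conditioning, Day 0, +14, +30, +100). Section 13.1.4 does not say which sample enters the model.
- False-positive rates of 16–19% (HR 0.83–0.86) arise only when the modelled level itself is capped at the limit, a 0.5 SD donor gap is assumed and the lead-in hazard is doubled. If the screening test has an assumed correlation of only 0.5 with the modelled level, the same case gives HR 0.89–0.92 and 8–10%.

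**Stakes.** No decision rule uses these models, and the comparison with historical patients already matches on donor type.

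**Conclusion.** The point holds for donor type. It is strongly prognostic on the protocol's own figures, recorded for every patient and used for matching in the same paragraph, yet it is absent from the named Cox terms.

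The possible harm is modest. For an assumed gap of 0.5 to 0.8 SD, the false HR per SD is about 0.91–0.95 with about 5–9% false positives in the two-year survival set-up. At the same gaps it is 0.87–0.92 with 6–8% if the outcome follows one-year NRM rates. These sizes rest on the assumed gap, on constant hazards, on the other-cause death rate in the survival set-up, and on carrying an NRM hazard ratio over to other outcomes. If level does not differ by donor type, the omission causes no bias.

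Only the secondary and exploratory association analyses are affected. The exact binomial test of one-year NRM does not use these models. The documents support a sensitivity analysis for lead-in membership, not a required term.

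**What to change.** In Section 13.1.4, state that Cox models for vitamin C level will include, or be stratified by, donor type (related vs unrelated) in addition to demographics; that the estimate without donor type will be reported beside it; and that safety lead-in membership will be added only in a sensitivity analysis.

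The cost is one sentence, no new data, one extra parameter and a standard error about 2–7% larger. With perhaps 19 to 28 events for acute GVHD the model can carry few terms, so the demographics should be a short list named in advance.
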